2.5.3 Exploratory Endpoints

The exploratory endpoints are:

1. Time to first nSEB.
2. The proportion of SEBs that undergo clinical resolution at Month 12.
3. The number of BCC surgeries from Baseline to Month 12.
4. Change in aBCCdex Worry About Future Lesions scale score from Baseline to Month 12.
5. Change in aBCCdex Mental Health scale score from Baseline to Month 12.
6. Change in aBCCdex Social/Relationships scale score from Baseline to Month 12.
7. Change in aBCCdex Life Impact scale score from Baseline to Month 12.
8. Change in Skindex-16 subscales (Symptoms, Emotions, and Functioning) from Baseline to Month 12
9. Change in Dermatology Life Quality Index (DLQI) total score from Baseline to Month 12
10. Shift in EuroQol (Quality of Life) using 5 levels (EQ-5D-5L) from Baseline to Month 12
11. Change in EQ-5D-5L Visual Analog Scale (VAS) from Baseline to Month 12

The time to first nSEB, defined as the date of first new SEB – date of randomization + 1, will be summarized using the Kaplan-Meier method. Subjects who do not develop an nSEB will be censored at the date of last tumor assessment, regardless of whether or not the subject was still on treatment. A Kaplan-Meier plot will also be provided.

The proportion of SEBs that undergo clinical resolution at Month 12 (or last assessment utilizing LOCF imputation) and the number of BCC surgeries will be summarized descriptively.

Change in Skindex-16 subscale scores and the DLQI total score will be summarized descriptively by visit. Please see Appendix B for the Skindex-16, and Appendix C for the DLQI.

A separate analysis plan for the pharmacokinetic data will be provided.

A shift table will be presented for changes from baseline of the EQ-5D-5L dimension scores. Additionally, the VAS Scores will be summarized descriptively by visit.

2.5.4 Interim Analysis

An Interim analysis was initially planned per protocol when all subjects have completed 6 months of treatment (or terminated the study earlier) and if at least 126 nSEBs have been observed. However, based on advice received during 1H 2020 interactions with FDA and EMA, and given both agencies' recommendation to not conduct the interim analysis, the option for an interim analysis was cancelled and the DMC disbanded prior to the original IA time point and prior to any unblinding; only a final analysis will be performed.

2.6 Safety Analyses

Dermal Safety and Tolerability

Shift tables of the frequency of dermal safety and tolerability assessments including pain/burning, pruritus, erythema, edema, and crusting will be summarized using counts and percentages by treatment group and visits of the most severe post baseline assessment and end of treatment from baseline.

A listing of all dermal safety and tolerability assessments will be provided.

Adverse Events

Subjects will be assessed for the occurrence of new and ongoing AEs from the time of informed consent. Descriptions of AEs will include the dates of onset and resolution (if resolved) including study days, maximum severity, seriousness, action taken regarding the treatment, corrective treatment, outcome, and Investigator's assessment of causality. All AEs will be recorded and classified using terminology from the MedDRA. AEs prior to treatment application will be summarized by preferred term. All reported treatment-emergent AEs (TEAEs), defined as any AE with an onset on or after the date of first treatment application and on or prior to the date of last application plus 30 days, or worsening of a condition with an onset prior to first treatment application and on or prior to the date of last application plus 30 days, will be summarized by treatment group, the number of subjects reporting TEAEs, system organ class, preferred term, severity, and relationship to treatment. Additionally, a summary of TEAEs by preferred terms will be provided for all preferred terms with at least 1 TEAE in the Patidegib arm. When summarizing TEAEs by severity or relationship to treatment, each subject will be counted only once within a system organ class or a preferred term using the event with the greatest severity or causality, respectively, within each category. All reported treatment-emergent Serious AEs (SAEs) will be summarized by treatment group, the number of subjects reporting SAEs, system organ class and preferred term as well as by preferred term. All reported TEAEs leading to treatment discontinuation (those TEAEs with action taken with study treatment of Drug Withdrawn) will be summarized by treatment group, the number of subjects reporting treatment-related TEAEs/TEAEs leading to treatment discontinuation, system organ class and preferred term as well as by preferred term. Additionally, paralesional TEAEs and TEAEs on complete area of treatment application will be summarized by preferred term.

AEs with a missing relationship to treatment will be classified as related to treatment. AEs with missing severity will be classified as severe.

All information pertaining to AEs (separately for AEs prior to treatment application and TEAEs) noted during the study will be listed by subject and will include a verbatim description of the event as reported by the Investigator, as well as the preferred term, system organ class, start date, stop date (if stopped), seriousness, severity, action taken regarding the treatment, corrective treatment, outcome and relationship to the treatment. In addition, separate listings of subjects who prematurely discontinue from

Pelle-926-301 Statistical Analysis Plan

17 June 2020

the study due to TEAEs, subjects who reported an AE leading to death, and subjects who experienced treatment-emergent SAEs will be provided.

Safety Laboratory Tests

Safety laboratory tests were initially intended to be done at one central laboratory (Clinical Reference Laboratory; CRL). However, since CRL decided to shut down its operations, midway through the study, laboratory testing has been migrated to a second laboratory (Cerba). Since two central labs will be used during the trial, the data from CRL will be normalized to the data from Cerba data using the methodology outlined in Karvanen (2003). The lab data from CRL will be normalized to the Cerba data by applying the following location-scale family transformation for each parameter using the female range if the ranges are different for males and females:

$$\text{normalized result} = L_{\text{Cerba}} + (x_{\text{CRL}} - L_{\text{CRL}}) * \left(\frac{U_{\text{Cerba}} - L_{\text{Cerba}}}{U_{\text{CRL}} - L_{\text{CRL}}} \right)$$

Where L_{Cerba} and L_{CRL} are the lower limits of normal of the parameter from Cerba and CRL, respectively, x_{CRL} is the result of the parameter for the subject, and U_{Cerba} and U_{CRL} are the upper limits of normal of the parameter from Cerba and CRL, respectively.

Then, if any normalized result for a given parameter is negative, then the scale family transformation will be applied instead:

$$\text{normalized result} = (x_{\text{CRL}}) * \left(\frac{U_{\text{Cerba}}}{U_{\text{CRL}}} \right)$$

Changes from Baseline to last on treatment in safety laboratory values, including chemistry and hematology, will be summarized separately with descriptive statistics in SI units for each treatment group at all applicable study visits. Separate listings for each panel will be provided.

Shift tables will be presented for changes in safety laboratory values to summarize laboratory test results from baseline to last on treatment. Normal ranges established by each of the central laboratories will be used to determine the shifts. A listing of all out-of-range laboratory test results at any assessment time point will also be provided. Determination of clinical significance for all out-of-range laboratory values, derived as any AE with a system organ class of Investigations, will be made by each Investigator and included in the listing. In addition, a listing of all clinically significant laboratory test results will be provided.

Pregnancy and urinalysis results will be provided in listings. A shift table for urinalysis results (normal vs. abnormal) from baseline to last on treatment will be provided.

Physical Examinations

Changes from Baseline for last on treatment in vital sign measurements will be summarized with descriptive statistics for each treatment group. A listing of vital signs results will be provided.

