1 SYNOPSIS

Sponsor:	PellePharm Inc [REDACTED]
Title:	A Multicenter, Randomized, Double-blind, Vehicle-controlled, Phase 3 Efficacy and Safety Study of Patidegib Topical Gel, 2%, for the Reduction of Disease Burden of Persistently Developing Basal Cell Carcinomas (BCCs) in Subjects with Basal Cell Nevus Syndrome (BCNS)
Short Title:	PATIDEGIB study
Protocol No:	Pelle-926-301
Study Regions:	United States (US), Canada, and European Union (EU)
Phase of Development:	Phase 3
Objectives:	
Primary Objective
 
 To assess the number of new BCCs in the 2 arms (Patidegib Topical Gel, 2%, and Vehicle) when applied twice daily to the face of subjects with Gorlin Syndrome 
Secondary Objective
 
 To assess the safety and tolerability of Patidegib Topical Gel, 2%, in subjects treated twice daily for 12 months
Study Design:	
This is a global, multicenter, randomized, double-blind, stratified, vehicle-controlled study of the efficacy and safety of Patidegib Topical Gel, 2%, applied topically twice daily to the face of adult subjects with Gorlin Syndrome.
 
Subjects will be randomized ([REDACTED]) to receive either Patidegib Topical Gel, 2%, or Vehicle for 12 months.
 
The assignment of subjects to the two groups will be stratified by gender, age ([REDACTED]), and previous Hedgehog inhibitor (HHI) therapy.
 
The primary endpoint is a comparison between the two treatment arms of the number of new BCCs that develop from Baseline to Month 12. BCCs will be imaged and tracked consistently throughout the study in order to identify new BCCs and new surgically eligible BCCs (nSEBs)
 
All subjects who complete the Month 12/Exit Visit having demonstrated adequate compliance with application of the Investigational Product (IP) without major Protocol Deviations (PDs) during the study will be eligible for participation in the open-label extension study.
 
All subjects will be contacted by phone approximately 30 days following the Exit or Discontinuation Visit to determine if the subject has experienced any new adverse events (AEs)/serious AEs (SAEs) since discontinuation/completion of study treatment.

Number of Subjects:	Approximately [REDACTED] subjects enrolled
Study Population:	Subjects of at least 18 years of age at the time of Screening with Gorlin Syndrome

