11.1.6 Reporting of Serious Adverse Events

SAEs will be captured in both the clinical and safety database.

All SAEs, regardless of cause or relationship, that occurs after the subject first consents to participate in the study (i.e., signs the informed consent) and throughout the duration of the study and for 30 days following the last IP application will be captured in the clinical database via the eCRFs (Section 11.1.2).

SAEs also will be captured in the safety database. An initial SAE Report must be completed for all SAEs (irrespective of relatedness) with an onset date within 30 days from the date of last IP application. An initial SAE Report must also be completed for Related SAEs (possibly, probably or definitely) regardless of the time elapsed from the last dose (even if the study has been closed).

When new, significant information for an SAE is obtained, as well as when the outcome of an SAE is known, the Investigator must submit a Follow-Up Report. If the subject was hospitalized, a copy of the discharge summary must be included as part of the subject's medical file. For related events, the Investigator should monitor the subject until the outcome of the SAE is known. This may require periodic Follow-Up Reports.

PellePharm and the study CRO must be notified of all SAEs (regardless of causal relationship to IP) within 24 hours of the Investigator's knowledge of the event by faxing or emailing a completed SAE report to the CRO Medical Monitor.

If there are serious, unexpected AEs associated with the use of the IP, PellePharm (or designee) will notify the appropriate regulatory agency(ies) and all appropriate parties as appropriate (e.g., IRB) on an expedited basis. It is the responsibility of the Investigator to promptly notify the IRB/IEC of all unexpected SAEs involving risk to human subjects.

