12.7.2 Adverse Events

Subjects will be assessed for the occurrence of new and ongoing AEs. Descriptions of AEs will include the dates of onset and resolution (if resolved), maximum severity, seriousness, action taken regarding the IP, corrective treatment, outcome, and Investigator's assessment of causality. All AEs will be recorded and classified using terminology from the MedDRA. All reported TEAEs, defined as any AE with an onset on or after the date of first IP application, or worsening of an AE with an onset prior to first IP application, will be summarized by treatment group, the number of subjects reporting TEAEs, system organ class, preferred term, severity, and relationship to IP. When summarizing TEAEs by severity or relationship to IP, each subject will be counted only once within a system organ class or a preferred term using the event with the greatest severity or causality, respectively, within each category. All reported SAEs will be summarized by treatment group, the number of subjects reporting SAEs, system organ class, preferred term, severity, and relationship to IP.

All information pertaining to AEs noted during the study will be listed by subject and will include a verbatim description of the event as reported by the Investigator, as well as the preferred term, system organ class, start date, stop date (if stopped), seriousness, severity, action taken regarding the IP, corrective treatment, outcome and relationship to the IP. In addition, a listing of subjects who prematurely discontinue from the study due to AEs will be provided as well as a listing of subjects who reported an SAE.

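### The SAP limits the SAE table and all but one AE listing to events before treatment or within 30 days of last application, so a non-fatal event recorded after that window is in no AE or SAE output

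*SAP*

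**What the plan says.** **Protocol.** Section 12.7.2 defines a TEAE by onset, or worsening, from first application and sets no upper time limit. On serious events it states: "All reported SAEs will be summarized by treatment group", broken down by system organ class, preferred term, severity and relationship. It adds a listing of subjects who reported an SAE. Section 11.1.2 requires AEs and SAEs to be reported from consent through the last study visit. Section 11.1.6 puts SAEs in the clinical database throughout the study and for 30 days after last application. The Synopsis has subjects "contacted by phone approximately 30 days following the Exit or Discontinuation Visit".

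**SAP.** Section 2.6 adds an upper limit to the TEAE definition: onset "on or prior to the date of last application plus 30 days". The SAE table is then restricted: "All reported treatment-emergent Serious AEs (SAEs) will be summarized by treatment group", by system organ class and preferred term, without severity or relationship. For earlier events, "AEs prior to treatment application will be summarized by preferred term". The by-subject listings are described thus: "All information pertaining to AEs (separately for AEs prior to treatment application and TEAEs) noted during the study will be listed by subject". Among the special listings, those for "subjects who reported an AE leading to death, and subjects who experienced treatment-emergent SAEs will be provided"; only the death listing has no treatment-emergent limit. Section 4, which sets out where the SAP overrides the protocol, records a change to the laboratory summaries but nothing on SAEs or the TEAE window.

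**The concern.** The protocol collects safety events over one period and the SAP reports them over a shorter one. The SAP's categories leave no place for an event that starts after treatment has ended and the 30-day cap has passed. A treatment-emergent cap is an ordinary choice for the TEAE tables. The difficulty is that the same cap also filters the SAE table, the SAE listing and the general AE listings, so nothing catches what it excludes.

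Safety and tolerability form the only secondary objective. The subjects affected are those who stop the gel some time before their Exit or Discontinuation Visit. Followed literally, the SAP would omit events that were collected, and the study report would not show that they had been. Separately, removing severity and relationship from the SAE table affects the presentation of every SAE, whenever it occurred.

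**Working it through.** The plan gives no figure on this point to reproduce. The first two steps compare text; the third sizes the gap.

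**Step 1. Can an event be recorded after the cap?** Let L be the date of last application and V the date of the Exit or Discontinuation Visit.

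- SAP cap: L + 30 days.
- Last study contact: about V + 30 days. The Schedule of Assessments includes AE collection at this call.
- Recorded time beyond the cap: (V + 30) − (L + 30) = V − L, plus any lateness of the call.

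For a subject who applies the gel up to the Month 12 visit, this is about zero. For a subject who stops earlier, it is the interval between stopping and the visit.

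**Step 2. Where does a non-fatal SAE with known onset after L + 30 appear?**

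| Output | Protocol 12.7.2 | SAP 2.6 |
|---|---|---|
| TEAE tables | Yes, no upper limit | No, past the cap |
| SAE table | Yes, all reported SAEs | No, treatment-emergent only |
| Pre-treatment AE table and listing | Not applicable | No, not pre-treatment |
| By-subject AE listing | Yes, all AEs | No, TEAEs only |
| SAE listing | Yes | No, treatment-emergent only |
| Death listing | Not applicable | Only if fatal |

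A late non-serious AE follows the same path. Under SAP Appendix D, a missing or incomplete onset date is treated as treatment-emergent unless other data indicate otherwise, so the gap concerns events with a known late onset.

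**Step 3. How many events?**

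- Early stoppers: 150 × 0.16 = 24 (SAP 2.2: about 150 randomised, 16% drop-out).
- Assumed gap V − L: mean 15 days if stops fall evenly between monthly visits; 30 days as the upper case.
- Assumed rates, which the documents do not give: 5 to 15 SAEs per 100 person-years and 2 to 5 AEs per person-year.

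| | 15-day gap | 30-day gap |
|---|---|---|
| Person-years | 24 × 15/365 = 0.99 | 24 × 30/365 = 1.97 |
| SAEs | 0.99 × 0.05 to 0.15 = 0.05 to 0.15 | 1.97 × 0.05 to 0.15 = 0.10 to 0.30 |
| AEs | 0.99 × 2 to 5 = 2.0 to 4.9 | 1.97 × 2 to 5 = 3.9 to 9.9 |

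These are totals over both arms. Taking the SAE count as Poisson, the 30-day case gives a chance of no affected SAE between exp(−0.30) = 0.74 and exp(−0.10) = 0.91. If all 24 stayed under follow-up off drug for a further 30 days, another 1.97 person-years would be added, and the 30-day figures would double.

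**The case against.** The strongest case on the other side is that the SAP window is legitimate and close to the protocol's own clinical-database window, that very few events fall outside it, and that other outputs cover part of the loss.

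- **Size.** Protocol 7.3 asks for evaluations at the time of early termination, so V may follow L closely. Protocol 7.4 ends data collection once a subject withdraws from the study. Both reduce the gap, possibly below the 15-day figure. This stands, and it is why the point is minor. In the other direction, SAP 2.4 reports treatment and study discontinuation separately, and the documents do not make clear how long a subject may remain in the study off drug.
- **Other outputs.** Fatal late events reach the death listing, and a late out-of-range laboratory value appears in the laboratory listing. An event that starts inside the window and later becomes serious remains a TEAE. All of this stands, but a non-fatal clinical event with late onset is still uncovered.
- **Reading of the listing sentence.** Its opening words cover all AE information, and the parenthesis could be read as describing only how the listings are split. The literal reading names two categories, and a programmer would build two.
- **Severity and relationship.** The TEAE tables keep both, and each listed AE carries seriousness, severity and relationship. For treatment-emergent SAEs the information can therefore be recovered from the listing, and little is lost.
- **Undeclared change.** The SAP, dated 17 June 2020, still has nSEBs as primary endpoint and cites a sample-size section number that the current protocol does not use. It appears to have been written against an earlier protocol whose AE wording is not available. It therefore cannot be shown that the narrowing was undeclared when written. The two documents do conflict as they stand.

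A reader might also infer that related SAEs reported long after treatment are lost from the analysis, because Protocol 11.1.6 says: "An initial SAE Report must also be completed for Related SAEs (possibly, probably or definitely) regardless of the time elapsed from the last dose". The documents do not support that as a fault of the SAP. The duty concerns the safety database and continues even after the study has closed. A final study table cannot be expected to hold such reports.

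**Conclusion.** The point holds and is minor. Under SAP 2.6 as written, a non-fatal AE or SAE with known onset later than 30 days after last application, but before the last study contact, appears in no AE or SAE table or listing. A fatal one appears only in the death listing. Protocol 12.7.2 would tabulate and list both, and SAP Section 4 does not reconcile the two.

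The expected loss is about 0.05 to 0.3 SAEs and 2 to 10 AEs over both arms. This rests on 24 early stoppers, a gap of 15 to 30 days and event rates that are assumptions. It would be smaller if discontinuation visits follow promptly or subjects withdraw from the study, and larger if subjects stay in follow-up off drug. A reader might infer that the study's safety conclusions are at risk; numbers of this size do not support that. What is shown is a reporting rule that discards collected data and is cheap to correct.

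**What to change.** In SAP 2.6:

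1. Summarise by arm all SAEs in the clinical database with onset from first application to the end of this study's follow-up, or to entry into the open-label extension if that comes first. Break them down by system organ class, preferred term, severity and relationship, with treatment-emergent SAEs as a marked subset. The extension cutoff keeps events under open-label exposure out of the randomised comparison.
2. Make the AE and SAE listings cover every recorded event, each flagged as pre-treatment, treatment-emergent or post-treatment.

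In SAP Section 4, record any narrowing that remains against Protocol 12.7.2, such as pre-treatment SAEs being listed but left out of the SAE table.

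The TEAE window itself can stay. The cost is a few sentences in the SAP, a revised SAE table and one flag in the listings. No further data collection is needed, and the SAP already has to be revised to match the current primary endpoint.

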12.7.4 Safety Laboratory Values

Changes from Baseline in safety laboratory values will be summarized with descriptive statistics for each treatment group at all applicable study visits.

Shift tables will be presented for changes in safety laboratory values to summarize laboratory test results collected at Screening to Baseline (Day 1) and at Months 1, 3, 6, 9, and Month 12/Exit Visit. Normal ranges established by the local laboratory will be used to determine the shifts. A listing of all out-of-range laboratory test results at any assessment

time point will also be provided. Determination of clinical significance for all out-of-range laboratory values will be made by each Investigator and reported as an AE accordingly. In addition, a listing of all clinically significant laboratory test results will be provided.

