3. DATA HANDLING

3.1 Baseline and Study Visits

Visits for all analyses will be as recorded on the electronic Case Report Forms. Baseline will be the latest of the non-missing values prior to receiving treatment. The following analysis windows will be used for all efficacy and safety data:

Visit	Target Day	Beginning of the Window	End of the Window
██████████	████	████	████
██████████	████	████	████
██████████	████	████	████
██████████	████	████	████
██████████	████	████	████

Note: All days are relative to the date of first treatment application.

If there is more than 1 assessment of the same data in the same window, then the latest assessment within the window will be used for analysis in the tables.

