4. CHANGES FROM THE PROTOCOL

This section highlights text in the SAP that overrides the cited text in the protocol.

The protocol (Section 8.2.1) refers to an Imaging Review Charter. In actuality this is an Imaging Review Work Instruction.

In the section on Sample Size Determination (Section 12.9) the protocol states ‘mean number of new **BCC** lesions at 6 months was 0.42’ instead of ‘mean number of new **SEB** lesions at...’

The secondary endpoints for the number of nSEBs at Months 6 and 9 were clarified to reflect that they are “by Month” 6 or 9 to bring these endpoints in line with the primary endpoint. Exploratory endpoints for the time to first nSEB, Skindex-16, DLQI, and EQ-5D-5L questionnaires were added.

The primary endpoint analysis distributional assumption was changed from Poisson to Negative Binomial based on FDA and EMA feedback, however the primary endpoint remains unchanged.

Pelle-926-301 Statistical Analysis Plan

17 June 2020

The interim analysis will no longer be performed based on EMA Scientific Advice, dated 26Mar2020, and FDA advice during a Type B Meeting held on 11May2020 recommending that the interim analysis should not be conducted; only a final analysis will be performed at an alpha level of 0.05 instead of 0.045 (both primary and secondary endpoints).

Laboratory test results will be summarized as change from baseline to last result on treatment instead of at each visit to provide a more concise, medically relevant summary.

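### Laboratory shift tables use only the last on-treatment value, so a transient out-of-range result not judged clinically significant reaches no by-arm shift count

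*SAP*

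**What the plan says.** **Protocol.** Section 12.7.4 plans descriptive laboratory changes by treatment group at every applicable visit. It also plans shift tables running from Screening to "Baseline (Day 1) and at Months 1, 3, 6, 9, and Month 12/Exit Visit". Section 8.3.3 requires an out-of-range result that the Investigator considers clinically significant to be recorded as an AE, and leaves repeat testing to the Investigator's discretion.

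**SAP 2.6, laboratory tests.** Three outputs are tied to the last on-treatment value:

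- Descriptive changes: "Changes from Baseline to last on treatment in safety laboratory values, including chemistry and hematology, will be summarized separately with descriptive statistics in SI units". The same sentence then continues "for each treatment group at all applicable study visits. Separate listings for each panel will be provided", which is by-visit wording.
- Chemistry and haematology shifts: "Shift tables will be presented for changes in safety laboratory values to summarize laboratory test results from baseline to last on treatment".
- Urinalysis: "A shift table for urinalysis results (normal vs. abnormal) from baseline to last on treatment will be provided".

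Out-of-range results at any time point go into a listing. No by-visit, any-time or worst-value laboratory shift table is planned.

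**SAP 4** declares the change: "Laboratory test results will be summarized as change from baseline to last result on treatment instead of at each visit". The reason given is a shorter and more medically relevant summary.

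**SAP 3.1** adds that if a window holds more than one assessment, "then the latest assessment within the window will be used for analysis in the tables".

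**SAP 2.6, dermal reactions.** Here the shift tables cover "visits of the most severe post baseline assessment and end of treatment from baseline", so a worst-value summary is kept.

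**Vital signs.** Protocol 12.7.3 plans changes at each applicable visit. SAP 2.6 gives change to last on treatment only, and SAP 4 does not mention vital signs.

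**The concern.** A last-value summary cannot show an effect that comes and goes. A result that is out of range at Month 3 and normal at Month 12 is tabulated as no shift. The protocol's own process makes a normal last value more likely, because clinically significant abnormalities are followed until they resolve or stabilise.

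Safety and tolerability over 12 months is the only secondary objective in both documents, and Protocol 6.1.3 gives the 12-month safety database as part of the case for the treatment duration. The comparison with vehicle is what separates a drug effect from background variation. A listing sorted by treatment holds the values but gives no counts or percentages by arm. What is at stake is a modest, transient laboratory effect spread over many subjects, each instance judged not clinically significant. It would not show up as a difference between arms in any planned count.

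**Working it through.** The plan states no figure to reproduce here, so the check sets the texts side by side and counts draws.

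**Step 1: time points in the by-arm tables.**

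| Output | Protocol 12.7.3 and 12.7.4 | SAP 2.6 |
|---|---|---|
| Laboratory shift tables | Months 1, 3, 6, 9, 12 (5 post-Baseline) | Last on treatment (1) |
| Laboratory descriptive changes | Every applicable visit | Last on treatment, with conflicting by-visit wording |
| Vital-sign changes | Every applicable visit | Last on treatment (1) |

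In a subject treated to Month 12, 5 − 1 = 4 post-Baseline results (Months 1, 3, 6 and 9) enter no by-arm laboratory shift table. The visit list is taken from Protocol 12.7.4 because the columns of the assessment schedule are misaligned in the text available. Its laboratory row has seven marks, which fits two pre-treatment and five post-Baseline draws.

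**Step 2: does the by-visit wording rescue it?** It conflicts with the opening of its own sentence and with SAP 4. Even read literally, it would give only by-visit means, SDs and medians: SAP 2.1 drops minimum and maximum for laboratory and vital-sign parameters. None of these counts subjects who went out of range.

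**Step 3: where a transient abnormality does appear.**

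- Judged clinically significant: recorded as an AE (Protocol 8.3.3) and tabulated by arm among the TEAEs (SAP 2.6).
- Not judged clinically significant: listing only.
- Still present at the last on-treatment draw: counted in the shift table either way.

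**Step 4: illustrative size, by assumption only.** The documents give no rate, duration or timing of abnormalities. Suppose a completer has one run of k consecutive abnormal draws among the five, with each possible position equally likely. There are 6 − k positions and exactly one includes Month 12, so the share missed by the shift table is (5 − k)/(6 − k):

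- k = 1: 4/5 = 80%
- k = 2: 3/4 = 75%
- k = 3: 2/3 = 67%
- k = 4: 1/2 = 50%
- k = 5: 0/1 = 0%

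An abnormality confined to Months 1 and 3 is always missed in a completer; one that persists to Month 12 never is.

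If a share c of abnormalities is judged clinically significant, the share with no by-arm count of any kind is (1 − c) × (5 − k)/(6 − k). For k = 1 this runs from 80% at c = 0 to 0% at c = 1. The value of c is unknown.

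**The case against.** **Clinically significant results are already compared by arm.** This stands, and it sets the limit of the point. A reader might infer that laboratory safety rests on one draw per subject, or that no transient effect could show a difference between arms. The documents do not support that, because the AE route operates at every visit.

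**An abnormality managed by interrupting the gel would be seen.** Largely true. Protocol 11.1.1 gives need for corrective treatment and leading to discontinuation as examples of clinical significance. The AE form records action taken on study product, and SAP 3.5 lists interruptions. If a subject stops while abnormal, that value may itself be the last on treatment.

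**A normal repeat could displace an abnormal value under SAP 3.1.** This cannot be sized. Repeat testing is discretionary, the window limits are redacted, and an abnormality that prompted a repeat because it was clinically significant should already be an AE. The rule matters here only because a worst-value table must be exempt from it.

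**The laboratory change is declared, with a reason.** True, so it is not an undisclosed departure. The reason explains brevity but not why laboratories lose the worst-value view that dermal reactions keep. The supplied protocol still promises the by-visit tables. SAP 4 also cites a sample-size section number (12.9) that differs from the supplied protocol's (12.8), so the two documents need aligning in any case.

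**Systemic effects are unlikely with a facial gel.** Protocol 6.2 reports no detectable plasma drug with the 2% gel in Phase 2, in a small study. This lowers the expected yield but does not remove the reason to tabulate data collected for the safety objective.

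**Conclusion.** The point holds in a limited form. By declared choice, the SAP replaces shift tables covering five post-Baseline visits with one based on the last on-treatment value, and it plans no worst-value laboratory table. The gap is confined to results that go out of range at Months 1 to 9, resolve before the last on-treatment draw, and are not judged clinically significant. Those have no by-arm count.

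The 4-of-5 figure should not be read as an estimate of lost safety information. It assumes a single abnormal draw, equal chance across visits, and treatment to Month 12. It falls as abnormalities persist, and it does not allow for those captured as AEs.

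For vital signs the same reduction is made without being declared in SAP 4. The efficacy analysis is not affected. This is a worthwhile, inexpensive improvement to the safety reporting rather than a flaw that undermines the trial.

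**What to change.** In SAP 2.6:

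1. Keep the last-on-treatment summaries and add by-arm shift tables from Baseline to the worst on-treatment value. For chemistry and haematology, show the highest and lowest values separately. For urinalysis, which is classed only as normal or abnormal, show normal to any abnormal.
2. Use all scheduled and unscheduled on-treatment results for these tables, and exempt them from the latest-in-window rule of SAP 3.1.
3. Reconcile the sentence on descriptive laboratory changes, so that it says either last on treatment or by visit, and align Protocol 12.7.4 and SAP 4 with the choice.
4. For vital signs, either restore the by-visit summary of Protocol 12.7.3 or add maximum and minimum on-treatment changes. Declare in SAP 4 whatever departure remains.

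The cost is SAP wording and one extra set of tables from data already collected. The downside is more out-of-range counts by chance in both arms, because several draws are searched for an extreme. These should be read against vehicle.
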